All statistical analyses were conducted using InStat 3.1a (GraphPad Software, La Jolla, CA). A modified intent-to-treat (ITT) population was used for analyses. For each outcome variable, the modified ITT population included all subjects with at least one post-baseline psychometric measurement (subjects received at least one week of aripiprazole). Demographic data is presented as means and standard deviations while bivariant data were contrasted using paired-t tests. A repeated measure analysis of variance (ANOVA) model was used to assess the changes in the psychometric tests. In cases where a subject did not complete the entire 6-week trial, the last available observation was carried forward (LOCF) and used for statistical comparisons. A repeated measure analysis of variance was used to assess the changes in the psychometric tests. For determining significance of statistical tests \langle was set at 0.05.

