Buitelaar et al (2001) assessed the efficacy of risperidone in the treatment of aggression. Thirty-eight adolescents were randomized to either risperidone or placebo in a double-blind fashion. The mean daily dose of risperidone at end of treatment (6 weeks) was 2.9mg [range = 1.5-4 mg]. Risperidone treatment produced improvement on the Clinical Global Impression-Severity (CGI-S) scale (LOCF, p<0.001) and the at-school Aberrant Behavior Checklist (ABC) overall and hyperactivity scales (p<0.05). In the risperidone group, following a 2-week washout following the 6-week trial worsening on all efficacy measures (CGI-S, Overt Aggression Scale-Modified (OAS-M), and the ABC. Weight gain was significant in the risperidone group (3.5% body weight increase, range – 1 to +6kg, p<0.05). Transient tiredness was also noted in 58% of drug-treated subjects, and was also the reason for dose reduction in five of the drug-treated subjects. Extrapyramidal Side Effect Rating Scale (ESRS) scores increased for Parkinsonism (cluster II) at endpoint compared to placebo (p<0.05).

Bellinghen et al (2001) compared risperidone (n=6) to placebo (n=7) in the treatment of behavioral disturbances in children and adolescents. Thirteen patients were enrolled in a 4-week double-blind, placebo-controlled study. Risperidone (mean dose = 0.05mg/kg; mean total dose = 1.2 mg/day) was more effective than placebo in improving ABC cluster scores for irritation and hyperactivity, the CGI scale. No significant differences in EPS symptoms or weight gain were seen between the treatment groups. The lack of any adverse effect differences is not surprising considering the low dose of risperidone and the small number of patients enrolled in the study.

Methods:

Dose and Schedule of Treatment: The proposed study will be a 6-week open label study evaluating aripiprazole in the treatment of 12 male post-pubertal adolescents (13-17 years, Tanner Stage 4) diagnosed with conduct disorder. The initial dose depending on the weight of the patient will be as follows: < 25 kg = 1 mg/d; 25-50 kg = 2 mg/d; 50-70 kg = 5 mg/d; > 70 kg = 10 mg/d (Data on File, 2003, Bristol-Myers Squibb). Thereafter the dose will be flexible based on response and tolerance.

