Main outcome measures: The primary outcome efficacy measures will be the Rating of Aggression Against People and/or Property Scale (RAAPP) (Kemph et al 1993), Overt Aggression Scale-Modified (OAS-M) (Kay et al 1988), and Children’s Aggression Scale-Parent Version (CAS-P) (Halpern et al 2002) while the secondary outcome measure will be the CGI severity and improvement scale (NIMH, 1985a). Safety measures for extrapyramidal adverse effects will include the AIMS (NIMH, 1985b) for tardive dyskinesia, Barnes Akathisia Scale (Barnes 1989) (BAS) and the Simpson-Angus Scale (SAS) (Simpson and Angus 1970). The UKU (Lingjaerde et al 1987) will be used for monitoring non-motor adverse effects. Height, weight and body mass index measurements as well as initial and endpoint fasting blood sugars and lipids will assess the effect of weight change. Obtaining serum prolactin levels as well as screening for the sexual dysfunction adverse effects including galactorrhea, gynecomastia, menstrual irregularities and changes in libido will assess sexual dysfunction adverse effects. An initial and endpoint ECG will be obtained to monitor patients for any changes in the QT-corrected interval. A gamma-GT will be collected to monitor liver function.

Schedule of Events:

Procedure	screening (-7 to -28days)	baseline	week 1	week 2	week 4	week 6
History-Demographics	X					
Physical Exam	X					X
ECG	X					X
Vitals, Height, Weight, BMI	X	X	X	X	X	X
Urine Collection	X					X
Phlebotomy	X					X
Dispense Study Drug		X	X	X	X	X
Determine medication compliance			X	X	X	X

Laboratory Tests

fasting glucose	X					X
fasting lipid profile:						
total cholesterol	X					X
HDL-cholesterol	X					X
LDL-cholesterol	X					X
Triglycerides	X					X
Prolactin	X					X
Gamma GT	X					X
CBC	X					X
Urine Drugs of Abuse Screen	X					X

Psychiatric Rating Scales

RAAPP		X	X	X	X	X
CAS-P		X	X	X	X	X
OAS		X	X	X	X	X
CGI-S		X	X	X	X	X
CGI-I			X	X	X	X

Side Effect Rating Scales

AIMS		X	X	X	X	X
SAS		X	X	X	X	X
UKU		X	X	X	X	X
BAS		X	X	X	X	X

References:

Buitelaar JK, van der Gaag, R, Cohen-Kettenis P, et al (2001). A randomized controlled trial of risperidone in the treatment of aggression in hospitalized adolescents with subaverage cognitive abilities. *J Clin Psychiatry* 62:239-48.

Barnes TRE (1989). A rating scale for drug-induced akathisia. *Br j Psychiatry* 154:672-6.

Data on File, 2003, Bristol-Myers Squibb Company, Princeton, NJ 08536

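### The SAP states no sphericity check or correction for its repeated-measures ANOVA, so the 0.05 level on each psychometric scale is not secured; the excess depends on correlations the documents do not give

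*SAP*

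**What the plan says.** The SAP is a single paragraph. It gives the method for the rating scales twice: "A repeated measure analysis of variance (ANOVA) model was used to assess the changes in the psychometric tests", and later "A repeated measure analysis of variance was used to assess the changes in the psychometric tests". The threshold sentence begins "For determining significance of statistical tests" and ends with a level that "was set at 0.05". The software is named ("All statistical analyses were conducted using InStat 3.1a") without any settings. Subjects who stop early have their last observation carried forward. Sphericity, an epsilon adjustment, a covariance structure and a planned contrast are not mentioned.

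The protocol's Methods section describes a "6-week open label study evaluating aripiprazole in the treatment of 12 male post-pubertal adolescents". In the Schedule of Events, the block headed "Psychiatric Rating Scales" has RAAPP, CAS-P, OAS and CGI-S at five times ("baseline week 1 week 2 week 4 week 6"). CGI-I starts at week 1. AIMS, SAS, UKU and BAS are listed in a separate side-effect block.

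**The concern.** The classical repeated-measures F test for visit is exact at its nominal level only under sphericity, meaning that the difference between any two visits has the same variance whichever two are chosen. That is doubtful here. Some ratings are one week apart and others six weeks apart, and if correlation weakens with time the longer differences vary more. The protocol also lets the dose vary with response and tolerance, so subjects may follow different trajectories, which breaks the condition too. The nominal degrees of freedom are then too large and the F test rejects too often.

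The trial has one arm and no control, so this within-subject test carries the efficacy inference. A p-value just under 0.05 on one scale could overstate the evidence. The problem sits inside each scale's own test, so a multiplicity rule across the three primary scales would not repair it.

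**Working it through.** **Inputs from the documents.** Level 0.05 (SAP). Planned n = 12 (protocol, Methods). Visit times t = 0, 1, 2, 4, 6 weeks, so k = 5 (protocol, Schedule of Events).

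**Assumptions.** All 12 subjects and all five visits enter the model; the SAP says neither. Data are normal with no true change. The documents give no covariance between visits, so a range was tried.

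**Test.** F = MS(visit) / MS(residual), referred to F with k − 1 = 4 and (k − 1)(n − 1) = 4 × 11 = 44 degrees of freedom. The 5% critical value is 2.58.

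**Step 1: the stated 5%.** Under equal correlations, 100,000 simulated trials rejected in 4.9% (Monte Carlo standard error about 0.07 percentage points). The plan's 0.05 is reproduced when sphericity holds.

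**Step 2: why decaying correlation matters.** Take unit variances and correlation ρ^|ti − tj|. The variance of a difference is 2(1 − ρ^gap). At ρ = 0.7 this is 2(1 − 0.7) = 0.60 for weeks 1 and 2, and 2(1 − 0.7⁶) = 1.76 for baseline and week 6. Sphericity needs these to be equal.

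**Step 3: size of the excess.** Box's epsilon is tr(A)² / [(k − 1) tr(A²)], where A is the doubly centred covariance matrix. It is 1 under sphericity and at least 1/4 here. Rejection rates at nominal 5%, n = 12, no dropout:

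| Assumed covariance | Epsilon | Unadjusted F | Greenhouse-Geisser |
|---|---|---|---|
| Equal correlation 0.5 | 1.00 | 4.9% | 3.1% |
| Decay, weekly 0.3 | 0.95 | 5.2% | 3.2% |
| Decay, weekly 0.5 | 0.86 | 6.0% | 3.6% |
| Decay, weekly 0.7 | 0.72 | 6.9% | 4.0% |
| Decay, weekly 0.8 | 0.64 | 7.6% | 4.3% |
| Decay, weekly 0.9 | 0.57 | 8.2% | 4.5% |
| Decay, weekly 0.95 | 0.53 | 8.7% | 4.8% |
| Random walk | 0.50 | 9.1% | 4.7% |
| Random slopes, SD 0.1 per week | 0.97 | 5.1% | 3.2% |
| Random slopes, SD 0.2 per week | 0.77 | 6.5% | 4.0% |
| Random slopes, SD 0.3 per week | 0.56 | 8.2% | 4.6% |
| Random slopes, SD 0.5 per week | 0.38 | 10.9% | 5.2% |

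The slope rows use a random intercept with SD 1 and residual variance 0.5.

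**Step 4: ceiling.** At the lower bound epsilon = 1/4, the rate is P(F(1, 11) > 2.58) = 13.6%.

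**Step 5: sensitivity.** With n = 10 the rates are almost the same. Last observation carried forward with 10%, 25% or 40% random dropout by week 6 moved the unadjusted rates by at most about 0.5 percentage points.

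**Step 6: effect on a borderline result.** An F of 2.58 gives p = 0.050 unadjusted. Multiplying both degrees of freedom by epsilon gives:
- epsilon 0.86: F(3.42, 37.7), p = 0.061
- epsilon 0.72: F(2.88, 31.6), p = 0.073
- epsilon 0.57: F(2.28, 25.1), p = 0.089

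**The case against.** Three stronger readings are tempting, and the documents support none of them.

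- **That the error rate simply is 6-9%.** That range belongs to one assumed family, decay at weekly correlation of about 0.5 or more. Other covariances give 5% or 11%, and nothing in the documents selects among them.
- **That the trial applied no correction.** The SAP is silent, and silence does not show that none was made. What the named software does by default cannot be settled from the documents. The same silence leaves a reader unable to tell which p-value is reported.
- **That unequal visit spacing is the fault.** Spacing alone does not break sphericity; with equal correlations and variances the test is exact at any spacing. Decaying correlation, unequal variances or differing slopes break it.

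It is also fair to say that the SAP applies the ANOVA to the psychometric tests and does not clearly extend it to the side-effect scales, so the point should stop at the former.

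The practical case against also has weight. Under decaying correlation the excess is about 1 to 4 percentage points, which matters only near 0.05. No adjustment lets an open-label single-arm study attribute change to the drug. Three primary scales at an unadjusted 0.05 would give 1 − 0.95³ = 14.3% if independent, which is a larger and separate issue. A paired t-test of baseline against week 6 held 4.8-5.1% under every covariance tried without dropout, and the SAP already names paired t-tests. These arguments limit the importance of the point. They do not make the F test, as written, secure its stated level.

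**Conclusion.** The point holds in conditional form. The SAP tests each psychometric scale at 0.05 by a method whose level depends on sphericity, and states neither a check nor a correction. With 12 subjects and five visits in the model, both taken from the protocol, the per-scale false-positive rate is:

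- 5% under equal correlations
- about 6-9% if correlation decays with time (assumed weekly 0.5-0.95)
- about 11% under strong subject-specific slopes
- never above 13.6%

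Where the trial falls in that range cannot be settled from the documents. A very small p-value would survive; one just under 0.05 might not. This is a worthwhile, inexpensive improvement and does not invalidate the analysis.

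**What to change.** In the SAP sentence on the psychometric tests, state that the repeated-measures ANOVA p-values for RAAPP, OAS-M, CAS-P and CGI-S use Greenhouse-Geisser adjusted degrees of freedom, and that the estimated epsilon is reported with each. Allow a second package if the named one does not provide the adjustment. State also which visits enter the model.

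The cost is one sentence and a re-run on the same data. The adjusted test stayed between 3.1% and 5.2% in the scenarios above. Its downside is mild conservatism at this sample size, about 3% if sphericity holds, so borderline p-values become slightly less favourable.

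### The efficacy scales get only an omnibus repeated-measures ANOVA on LOCF-filled scores, with no stated baseline-to-week-6 estimate

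*SAP*

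**What the plan says.** The Protocol (Methods, Dose and Schedule of Treatment) describes a "6-week open label study evaluating aripiprazole in the treatment of 12 male post-pubertal adolescents". Main outcome measures names three primary scales (RAAPP, OAS-M, CAS-P). The Schedule of Events has each rated at baseline and weeks 1, 2, 4 and 6, so there are five time points. No primary time point or summary measure is given.

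The SAP is a single paragraph. On the efficacy scales it says, and then repeats almost word for word: "A repeated measure analysis of variance (ANOVA) model was used to assess the changes in the psychometric tests". On missing data: "In cases where a subject did not complete the entire 6-week trial", "the last available observation was carried forward (LOCF) and used for statistical comparisons". On the analysis set: "the modified ITT population included all subjects with at least one post-baseline psychometric measurement". It also says that "bivariant data were contrasted using paired-t tests", in the sentence on demographics, without naming the variables or the visits compared. No contrast, post-test, effect estimate, confidence interval, sphericity correction or sensitivity analysis is named.

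**The concern.** Readers of a 6-week trial will take its result as the change after 6 weeks. The plan does not promise that quantity, for three reasons.

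- **Question asked.** With no contrast named, the ANOVA yields an F test of whether any of five visit means differ, in either direction. That is neither an estimate of the week-6 change nor a test of it.
- **Missing data.** One post-baseline score is enough for inclusion. A subject seen only at week 1 therefore contributes that score again at weeks 2, 4 and 6. This understates a response that is still building and preserves one that later fades. Dosing is flexible after the initial dose, so scores may well still be moving after week 1. There is no control arm to offset the error; it falls directly on the pre-post change.
- **Sphericity.** The uncorrected F holds its 5% level if all visits are equally correlated, but not if correlation decays with time.

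**Working it through.** **Inputs.** From the documents: n = 12, one arm, visits at weeks 0, 1, 2, 4 and 6, alpha 0.05. They give no power calculation, SD, dropout rate or trajectory, so there is no planned figure to reproduce and what follows is illustrative.

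Assumptions: SD 1 at each visit; everyone seen at week 1; 2 of 12 (17%) or 4 of 12 (33%) lost after weeks 1, 2 or 4; dropout either random or more likely in non-improvers (logit hazard slope 1.5 per SD of current change). Three correlation structures: constant 0.6; 0.7^weeks; and a 40% shared subject part plus 0.7^weeks for the remainder. Simulations use 20,000 trials per scenario. Gains are reductions in score.

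**1. LOCF when response is still building.** With a linear gain of 0.90 SD, a subject last seen at week w lowers the mean by 0.90 × (1 − w/6) / 12:

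- week 1: 0.90 × 0.833 / 12 = 0.063 SD (7%)
- week 2: 0.90 × 0.667 / 12 = 0.050 SD (6%)
- week 4: 0.90 × 0.333 / 12 = 0.025 SD (3%)

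If losses are spread evenly over those weeks, the average is (0.0625 + 0.050 + 0.025)/3 = 0.0458 SD per dropout. The expected result is then 0.90 − 2 × 0.0458 = 0.81, or 0.90 − 4 × 0.0458 = 0.72. Simulated LOCF means:

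| True change 0.90 SD | Lost | Random dropout | Non-improvers leave more often |
|---|---|---|---|
| Linear | 0 of 12 | 0.90 | – |
| Linear | 2 of 12 | 0.81 | 0.72–0.76 |
| Linear | 4 of 12 | 0.71 | 0.55–0.63 |
| Plateau by week 2 | 2 of 12 | 0.87 | 0.78–0.83 |
| Plateau by week 2 | 4 of 12 | 0.84 | 0.68–0.76 |

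**2. LOCF when an early response fades.** Take a dip of 0.8 SD at weeks 1 and 2, 0.4 at week 4 and zero at week 6. A dropout carries forward (0.8 + 0.8 + 0.4)/3 = 0.667 SD on average, so the false week-6 benefit is 2/12 × 0.667 = 0.11 or 4/12 × 0.667 = 0.22 SD. Simulation gives 0.11 and 0.23 under random dropout, and 0.02–0.06 and 0.07–0.14 if non-improvers leave more often.

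**3. What the F test detects.** Same dip, no dropout. The visit means are 0, −0.8, −0.8, −0.4, 0 (average −0.4), with sum of squares 4 × 0.16 = 0.64. With constant correlation 0.6 the noncentrality is 12 × 0.64 / (1 − 0.6) = 19.2. On 4 and 44 df (critical value 2.58) the F test rejects 93% of the time, although nothing has changed at week 6. Across the three structures:

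| Size of dip (SD) | Omnibus F significant |
|---|---|
| 0.3 | 16–23% |
| 0.5 | 35–56% |
| 0.8 | 77–95% |
| 1.0 | 94–100% |

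The baseline-to-week-6 contrast stays at 5% throughout.

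**4. Sphericity.** Over a wider range of correlations (constant 0.3–0.8; decay base 0.5–0.9, with and without a shared part of 0.4–0.6), the uncorrected F has type I error 5.0–5.1% with constant correlation and 5.9–8.3% with decaying correlation. Greenhouse-Geisser gives 3.2–4.4%.

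**5. The replacement model.** A random intercept plus spatial-power covariance, fitted by REML with Kenward-Roger degrees of freedom (the variance adjustment computed without its second-derivative term), was run on 24 scenarios × 1,500 = 36,000 datasets of 12 subjects. None failed to fit. For a true 0.90 the mean estimate was 0.88–0.94, with 95% CI coverage of 92.5–96.5%. Type I error was 5.2–6.1% with 0–2 of 12 lost and 3.5–7.5% with 4 of 12 lost (Monte Carlo SE about 0.6 points). Spatial power alone gave 0.4–5.7%, conservative when correlation is constant.

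**The case against.** The best defence is that the LOCF error is conditional and often small beside the sampling error. The standard error of a 12-subject change is √(2(1 − r)/12), with r the baseline-to-week-6 correlation: 0.26 SD for r = 0.6 and 0.38 SD for r = 0.7^6 = 0.12. Losing 2 of 12 at random costs 0.09 SD, about a quarter to a third of that. A paired week-6 t interval on LOCF data still covers 93–94% of the time. With no true change at any visit, false claims of benefit run at 0.7–2.6% against a nominal 2.5%. All this stands. Serious loss needs about 4 of 12 lost while scores are still moving (coverage 85–91%), and nothing in the documents predicts a transient dip.

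The word omnibus is an inference from the absence of any named contrast, and the paired t-tests may have been meant for baseline against endpoint. That is possible. They would still use LOCF values for dropouts and come with no stated estimate.

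The mixed model is not clearly better on type I error when 4 of 12 are lost, and its covariance form is a choice. It was tested only where dropout depends on observed scores, which favours it. These limits are real. Comparing LOCF with observed cases would be simpler, but the observed-case mean is itself biased when non-improvers leave more often: 0.99–1.18 for a true 0.90.

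Finally, this is a small open-label study without a confirmatory claim. That lowers the stakes, but it makes a plain estimate with its uncertainty more useful than an F test.

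**Conclusion.** The concern holds and should be fixed. The absence of a stated week-6 contrast, estimate and confidence interval follows from the text alone and does not depend on dropout. It is the core of the point.

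The LOCF distortion is conditional: zero without dropout, and small if response plateaus early and dropout is random. In the linear scenarios it takes 0.09 to 0.35 SD off a true 0.90 SD (0.90 − 0.81 to 0.90 − 0.55). It can also run the other way when an early response fades. Sphericity is the minor part, at most about 3 percentage points of type I error (8.3% against 5%). All sizes rest on assumed trajectories, correlations and dropout.

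**What to change.** Replace the ANOVA and LOCF sentences of the SAP with:

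> Each aggression scale is analysed with a linear mixed model on all observed scores, with visit as a categorical fixed effect, a random intercept plus spatial-power within-subject covariance, REML and Kenward-Roger degrees of freedom. The main efficacy result is the baseline-to-week-6 change with its 95% CI. Sensitivity analyses: spatial-power covariance alone, and LOCF.

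Also:

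- Report how many subjects were last seen at weeks 1, 2 and 4.
- Apply a Greenhouse-Geisser correction to any ANOVA that is kept.
- Say which variables and visits the paired t-tests cover.
- The SAP is written in the past tense. If the data have already been analysed, label this a reanalysis.

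**Cost.** SAP text, and another package if InStat cannot fit mixed models. It uses scores already in the Schedule of Events, so no new data or patients are needed. The model assumes data missing at random, and its type I error can reach about 7.5% if 4 of 12 drop out. It does not supply a comparator: neither analysis separates a drug effect from placebo response or regression to the mean.
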